7.0 PRODUCT DESCRIPTION	
• Page 20 (page 20 in CIP version 1.0):	
"polymethymethacrylate" has been	
corrected to	
"polymethylmethacrylate".	
8.0 SELECTION OF SUBJECTS	
• Page 23 and 24 (nage 23 and 24 in CIP	
v1.0): scoliosis, kyphosis and lordosis	
have been removed from the	
examples of deformity indications.	
Dage 22 (page 22 in CID version 1 0);	

 
rage 25 (page 25 III CIP Version 1.0):
 
The sentence "one of the following
 
	
conditions" has been replaced with	
conditions has been replaced with	

#MDT17040SD1703

Version 2.0/ 19 SEP 2018

Page 65 of 65

Medtronic

## 1. Version History

Version	Summary of Changes	Author(s)/Title
1.0	

Not Applicable, New Document

	[name], Principal Statistician
2.0	

Introduction: Added a statement regarding the change of the study objective and reasons behind the change.

Study Objectives: Objectives were not divided into Primary and Secondary Objectives. The following objectives, including neurological success, radiographic assessment of stabilization of the pedicle screw instrumentation, radiographic fusion status, and changes in coronal and sagittal spinopelvic parameters, were removed. The endpoint analyses at 24-month visit were removed.

Investigational Plan: Removed the language regarding 100 subjects with two indication groups (50 each) to be enrolled in 10 investigational sites. Removed the requirement for data collection at 12- and 24-month visits. Limited the scope of the data collection to VAS back and leg pain, ODI, EQ-5D 5L, and adverse events and/or device deficiencies.

Determination of Sample Size: Removed the descriptions about how the sample size was calculated. Added a language stating that the number of the anticipated available subjects will be around 20.

Analysis Datasets: Datasets were not separated into Primary Analysis Dataset and Per-Protocol Analysis Dataset. Added the language stating that for subjects who already had a data collection beyond 3 months at time of the premature termination announcement, the data beyond 3 months will be summarized, and for the subjects who enrolled and underwent surgery but will not be able to complete 3-month follow-up visit by the scheduled study closure, they will be included in the analysis.

Definition of Time Periods: Removed 24 months from the definition and the language about the life table method of the time-to-event analysis.

Clinical Data and analysis: Removed the requirement of analysis for spinopelvic parameters, neurological status, and medication use. Removed the time-to-event analysis method.

Center Pooling: Changed 10 study sites to 6 study sites.

	[name], Principal Statistician

# FNS Study Statistical Analysis Plan

Revision [2.0]

Page 4 of 14

Form

Medtronic

Version	Summary of Changes	Author(s)/Title
	

• Interim Analysis: Deleted the requirement for an interim analysis.

• Evaluation of Objectives:

1. Deleted the subtitles "Primary Objective and Analysis" and "Secondary Objectives and Analyses".

2. Removed Analyses for ODI improvement, VAS back and leg pain improvement, and EQ-5D 5L improvement at 24 months. Defined "Improved" and "Not Improved" in each clinical measure. Added the language for summary of "Improved" and "Not Improved" subjects.

3. Deleted requirements of analyses for neurological success, stabilization of pedicle screw instrumentation, radiographic fusion status, and changes of coronal and sagittal spinopelvic parameters.

4. Added the Section 7.9.8 of Data Listing for neurological status, stabilization of pedicle screw instrumentation, fusion status, and spinopelvic parameters.

• Changes to Planned Analysis: Modified the statement "No changes have been made to the original planned analyses..." to "Changes have been made to the original planned analyses...".

	

## 2. List of Abbreviations and Definitions of Terms

Abbreviation	Definition
ADE	Adverse Device Effect
AE	Adverse Event
CIP	Clinical Investigation Plan
DD	Device Deficiency
EC	Ethics Committee
EQ-5D 5L	European Quality of Life – 5 Dimension, 5 Levels
FDA	U. S. Food and Drug Administration
FNS	Fenestrated Screws
PIC	Patient Informed Consent
IFU	Instructions for Use
ODI	Oswestry Disability Index
PMMA	Polymethylmethacrylate
SADE	Serious Adverse Device Effect
SAE	Serious Adverse Event
USADE	Unanticipated Serious Adverse Device Effect
VAS	Visual Analog Scale

## 3. Introduction

CD HORIZON® Fenestrated Screws (FNS) Spinal System with Fenestrated Screw Cement is a thoracolumbar surgical device for the treatment of degenerative disc disease, ankylosing spondylitis, spondylolisthesis, trauma, spinal stenosis, curvatures (scoliosis, kyphosis or lordosis), tumor, and failed previous fusion (pseudoarthrosis) in Europe. In US, it has been approved for the treatment of the patients with advanced stage tumors only. The surgery utilizes pedicle screws and rod systems for posterior stabilization and immobilization of the thoracolumbar spine. Compromised bone is prone to poor screw anchorage resulting in screw loosening, screw pullout, screw toggle, and/or complete hardware failure. Therefore, the success of the surgery depends on how strong the fixation of pedicle screws within the vertebrae of a spinal segment is.

Bone cement consisting of polymethacrylate (PMMA) has been widely used for implant fixation in various surgeries. In CD HORIZON® FNS Spinal System, an FNS screw is cannulated at center and contains six fenestrations (openings) at the distal end of the screw. The bone cement is injected through a continuous tract in the adapter and into the screw cannula. The cement is extruded through those fenestrations into the targeted vertebral body in a controlled manner. The self-curing PMMA cement serves as the screw interface and provides holding power of the screws. It has been shown to significantly increase the screw pull-out strength. As a result of the cement-augmented pedicle screw fixation, the procedure improves clinical outcomes resulted from spinal diseases such as spinal stenosis. One of the side effects associated with the application of bone cement is potential cement extravasation which could lead to clinical complications. The risk, however, can be reduced through various measures such as improved accuracy of the cement delivery.

CD HORIZON® Fenestrated Screws (FNS) Spinal System has been CE-marked since 2011 for the treatment of a wide range of spinal diseases including degenerative disc disease, spondylolisthesis, etc., and received 510(k) clearance from FDA since 2016 for the treatment of the patients diagnosed with advanced stage cancers involving the thoracolumbar spine. The initial objective of this proposed study was to evaluate the safety and effectiveness of CD HORIZON® Fenestrated Screws (FNS) Spinal System with Fenestrated Screw Cement for stabilization and immobilization of spinal segments in subjects with compromised bone quality, and to support FDA 510(k) application for expanded indications in US. However, the objective has been changed and the study will be prematurely terminated one year after the study was initiated due to the following reasons: A. Expanding the indications in the US for Fenestrated Screws with Fenestrated Screw Cement is no longer a business priority; B. Alternative data sources to support the products and regulatory submission are available; C. Current slow enrollment significantly protracts the timeline for study completion, which will result in significant increase in the study budget. The initial proposed study was a prospective, multicenter, and post-market clinical trial for 100 subjects with degenerative spinal disease or deformity to be treated at one to multiple thoracolumbar levels located from T1 to S2. The premature termination of the study will stop further enrollment of patients, but the study will continue to follow-up the already enrolled patients until the 3-month follow-up visit with a visit cut-off of 15 July 2020. This new version of SAP is intended to make adjustment for the objectives and endpoints defined in the initial SAP as a result of the premature termination of the study.

## 4. Study Objectives

The objective is to assess the following endpoints for subjects with compromised bone quality, who will receive a surgical procedure requiring posterior stabilization and/or immobilization of one or more spinal segments using CD HORIZON® Fenestrated Screw Spinal System with Fenestrated Screw Cement:

- Improvement of ODI at 3- and 12-month visits from baseline;
- Improvement of VAS back and leg pain score at 3- and 12-month visits from baseline;
- Improvement of EQ-5D 5L at 3- and 12-month visits from baseline;
- Intraoperative cement extravasation/leakage;
- Device and/or procedure related adverse events up to 3- and 12-month visits;
- Secondary spinal surgeries at index and/or adjacent level(s) up to 3- and 12-month visits.

## 5. Investigation Plan

This is a prospective, single-arm, multicenter study involved in the treatment of subjects with compromised bone quality using CD HORIZON® Fenestrated Screw Spinal System with Fenestrated Screw Cement in Europe. All subjects participating in this study will be required to sign a Patient Informed Consent (PIC) form which must be approved by the Ethics Committee (EC) before enrollment.

The enrollment will be cut off when the anticipated decision of the premature termination is announced to the investigators. The data of the available enrolled and treated subjects across current 6 investigational sites in Europe will be collected from baseline to 3-month (and 12-month if available) postoperative follow-up visit(s). There may be more than one pre-planned surgery for the treatment procedure. The pre-planned secondary surgery should be conducted within 3 months following the initial surgery. There should be at least 1 month in between the pre-planned secondary surgery and 3-month follow-up visit to reduce any bias on the patient reported outcomes. The pre-planned secondary surgery should not be reported as an adverse event. The initial surgery date will be used to determine the time period for an adverse event as described in the section 7.2.1.

Data will be collected at baseline, surgery, postoperative period prior to hospital discharge, and postoperative visits at 3 months and 12 months (if available). At baseline, data collected for analysis include medical and surgical history, conservative care types, indications to be treated, demographics, VAS back and leg pain, ODI, and EQ-5D 5L. During surgery, the following data are collected for analysis: surgery time, blood loss, number of levels treated, procedure types, devices and their components (such as screws and cement), intraoperative cement extravasation/leakage, and adverse events and/or device deficiencies. At postoperative assessment prior to hospital discharge, the data collected for analysis include adverse events and/or device deficiencies. During postoperative visits at 3 months and 12 months (if available), the following data will be collected for analysis: VAS back and leg pain, ODI, EQ-5D 5L, secondary spinal surgeries, and adverse events and/or device deficiencies.

## 6. Determination of Sample Size

The initial sample size with 100 subjects was calculated based on the defined primary endpoint (i.e. improvement of ODI at 12 months from baseline). Due to the premature termination of the study, the number of available subjects is anticipated to be around 20. These are the ones already enrolled at time of announcement of the study termination and continued to be followed up until the visit cut-off of 15 July 2020.

## 7. Statistical Methods

### 7.1 Study Subjects

#### 7.1.1 Disposition of Subjects

The study subjects will include those who have signed the Informed Consent and underwent surgery. Subjects are scheduled to be followed up to the visit cut-off date (15 July 2020) after index surgery. During the follow-up period, a subject can voluntarily withdraw from the study at any time and for any

reason. The site investigator can only withdraw a subject from the study with a valid reason. The following may be some of the reasons for withdrawal or exit of a subject: PIC procedure not followed, eligibility criteria not met, death, subject voluntary withdrawal from the study, and the fenestrated screw procedure defined in CIP not followed. For the lost to follow-up subjects, the site investigator should make every effort to contact the subject. At least three contact attempts should be made via phone calls, text messages and/or emails.

With the visit cut-off date of 15 July 2020, it is expected that the majority of the subjects who enrolled and treated, if not all, would be followed up through 3 months after surgery. It is also expected that two subjects will complete the 12-month follow-up visit.

### **7.1.2 Protocol Deviations**

A study protocol deviation exists if any one or more following conditions are met:

- PIC procedure not followed;
- Inclusion/Exclusion criteria not met;
- Visit not done;
- Required assessment(s) at the visit not performed;
- Visit fallen outside the CIP defined visit window;
- The fenestrated screw procedure not followed as defined in this protocol;
- Improper AE / SAE / ADE / SADE / DD reporting;
- EC approval not obtained, if required.

### **7.1.3 Analysis Datasets**

Analysis will be conducted for the subjects who are enrolled in the trial, undergo the designated surgical procedure, and receive the treatment of the CD HORIZON® Fenestrated Screw Spinal System with Fenestrated Screw Cement. The subjects who are enrolled but do not receive intended medical devices (such as competitor's screws and/or cement) will not be included in analysis. The missing data will not be imputed, and all analyses will be based on the observed data. For the subjects who already had a data collection beyond 3 months at time of the premature termination announcement, the data from beyond 3 months will be summarized. For those who enrolled and underwent surgery but will not be able to complete 3-month follow-up visit by the scheduled study closure, the data, if available, will be included in the analysis.

## 7.2 General Methodology

### 7.2.1 Definition of Time Periods

For analysis on adverse events and secondary spinal surgeries, time periods used in this study are defined in Table 1.

**Table 1: Time Periods Used for Summaries of AEs and Secondary Spinal Surgeries**

Time Period	Duration (Days*)
Operative	0 day
1 Day to 4 Weeks	$\geq 1$ Day and $< 28$ days
6 Weeks ( $\geq 4$ weeks and $< 2$ months)	$\geq 28$ days and $< (2 \times 30.4 - 1)$ days
3 Months ( $\geq 2$ months and $< 5$ months)	$\geq (2 \times 30.4 - 1)$ days and $< (5 \times 30.4 - 1)$ days
6 Months ( $\geq 5$ months and $< 9$ months)	$\geq (5 \times 30.4 - 1)$ days and $< (9 \times 30.4 - 1)$ days
12 Months ( $\geq 9$ months and $< 19$ months)	$\geq (9 \times 30.4 - 1)$ days and $< (19 \times 30.4 - 1)$ days

\* Days = Event Onset Date – Index Surgery Date. For subjects with a pre-planned second surgery, the initial surgery date is used as the index surgery date.

### 7.2.2 Clinical Data and Analyses

For continuous clinical outcome scores such as ODI score, VAS back and leg pain score and EQ-5D 5L, the summary statistics (n, mean, median, standard deviation, minimum and maximum) at the postoperative time point will be presented. The changes at postoperative visit(s) from preoperative will be analyzed using paired t-test for normally distributed data or Wilcoxon signed-rank test for not normally distributed data where the test is appropriate.

For categorical clinical outcomes such as the sex of subjects, frequency and percentage of subjects will be summarized at postoperative time point(s).

For AEs and secondary surgeries, the number of events and subjects at each time period as well as the rate up to 3 months and 12 months will be summarized.

The summary results of the two indication subgroups (degenerative disc disease and deformity) will be presented where appropriate.

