### **7.9.5 Device and/or Procedure Related Adverse Events**

Adverse events (AEs) will be independently assessed by the site investigators and the sponsor, Medtronic, plc. If an adverse event is determined to be related to any of the following device components, then the event is said to be device related:

- Access system
- Cage/Interbody
- Anterior plate
- Bone grafts and substitutes
- Rod system
- Fenestrated screws
- Fenestrated screw cement
- Other components of the Fixation (Stabilization) System

The causality of AEs is classified into the following categories:

- Not related
- Unlikely
- Possible
- Probable
- Causal relationship

For a conservative consideration, an adverse event with a possible, probable or causal relationship is considered as device and/or procedure related. AEs at individual time intervals as well as cumulative up to 3 months and 12 months will be summarized.

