### **7.9.6 Secondary Spinal Surgeries**

Secondary spinal surgical procedures resulted from AE(s) can be classified into four categories: revision, removal, reoperation, and other. Secondary spinal surgeries at index and/or adjacent levels at individual time intervals as well as cumulative up to 3 months (and 12 months if available) will be summarized. Although the use of external bone growth stimulators (BGS) is not considered as a secondary spinal surgical procedure, it will be recorded in the database and summarized.

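### SAP 7.2.2 promises a 12-month rate of adverse events and secondary surgeries without a denominator or a rule for unequal follow-up, when about 2 of 20 subjects are expected to reach 12 months

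*SAP*

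**What the plan says.** SAP 7.2.2 deals with adverse events and secondary surgeries together. Its wording is: "number of events and subjects at each time period as well as the rate up to 3 months and 12 months will be summarized". SAP 7.9.5 adds for adverse events: "AEs at individual time intervals as well as cumulative up to 3 months and 12 months will be summarized"; it does not call this a rate. The objectives in SAP 4 list "Device and/or procedure related adverse events up to 3- and 12-month visits" and "Secondary spinal surgeries at index and/or adjacent level(s) up to 3- and 12-month visits". None of these passages limits the 12-month figure to data that exist.

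Other sections do. SAP 5 reads "During postoperative visits at 3 months and 12 months (if available), the following data will be collected for analysis". SAP 7.9.6, on secondary surgeries, promises summaries that are "cumulative up to 3 months (and 12 months if available) will be summarized", and SAP 7.9.7 does the same for serious adverse events.

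On numbers, SAP 6 says "the number of available subjects is anticipated to be around 20", and SAP 7.1.1 says "It is also expected that two subjects will complete the 12-month follow-up visit". SAP 3 plans follow-up of enrolled subjects to the 3-month visit, with a cut-off of 15 July 2020. SAP 7.1.3 takes all subjects who had the surgery and received the study device, including those who cannot complete the 3-month visit. SAP 7.1.3 and 7.4 rule out imputation. Protocol 13.1 had planned a time-to-event estimate for both endpoints. The current SAP has none and puts no other rule in its place.

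**The concern.** A rate up to 12 months needs either 12 months of observation on everyone in the denominator or a method that allows for shorter follow-up. Stopping at one calendar date makes follow-up unequal by design, so the missing rule matters more than it would have in the full study. Whoever programs the tables must choose a denominator, and the obvious choices give very different figures from the same data. The published number could be quoted as a 12-month safety result that the follow-up cannot support.

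The SAP has already met this problem elsewhere. Section 7.9.8 replaces summaries of the 12-month neurological and radiographic endpoints with listings because only two subjects will get that far. The 12-month safety rate was kept.

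**Working it through.** The plan gives no computed figure for this rate, so there is none to reproduce.

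**Inputs from the documents.** About 20 subjects (SAP 6); two 12-month completers (SAP 7.1.1); most, if not all, followed through 3 months (SAP 7.1.1).

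**Assumptions, not in the documents.** All 20 are treated; the other 18 leave at c months, with c from 3 to 6, or with exits spread evenly over 3 to 12 months.

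**Step 1: observed time.** Full follow-up would be 20 × 12 = 240 person-months. Observed time is 18c + 24.

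| Exit of the 18 | Observed to month 12 | Observed in months 3 to 12 |
|---|---|---|
| c = 3 | 78 of 240 (32.5%) | 18 of 180 (10%) |
| c = 6 | 132 of 240 (55%) | 72 of 180 (40%) |
| even over 3 to 12 (mean 7.5) | 159 of 240 (66%) | 99 of 180 (55%) |

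**Step 2: all-treated denominator.** Let F(t) be the true risk of at least one event by month t. The expected crude proportion is [2F(12) + 18F(c)]/20. With s = F(c)/F(12), crude/true = 0.1 + 0.9s.

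| s | crude/true |
|---|---|
| 0.25 | 0.325 |
| 0.5 | 0.55 |
| 0.75 | 0.775 |
| 0.9 | 0.91 |
| 1 | 1.00 |

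The ratio is below 1 whenever s is below 1, so the direction needs no assumption about the shape of the hazard. With 18 or 22 treated instead of 20, these ratios move by at most 0.01.

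As an illustration, take a true 12-month risk of 20% (assumed). Under a constant hazard, F(3) = 1 − 0.8^(3/12) = 5.4%, and the crude rate is (2 × 0.20 + 18 × 0.0543)/20 = 6.9%. For c = 6, F(6) = 10.6% and the crude rate is 11.5%. If 90% of the risk falls by month 3, the crude rate for c = 3 is 0.91 × 20% = 18.2%.

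**Step 3: completers-only denominator.** With n = 2 the proportion of subjects with an event can only be 0, 50% or 100%. For 0/2 the exact 95% CI runs from 0 to 84.2%.

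**Step 4: how far the choices differ.** One subject with an event at month 8, a completer, and no earlier events: 1/20 = 5% on all treated, 1/2 = 50% on completers. A life table with only the two completers still at risk also gives 50%.

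**Step 5: would a time-to-event estimate to 12 months rescue it?** Simulation with a constant hazard, true risk 20%, and 18 leaving at month 3 gives a life-table mean of 19.8%, so the bias is gone. The standard deviation is about 25 percentage points, so the estimate is of little use.

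**Step 6: the 3-month rate.** It is affected less, but its end day is open. SAP 4 ties it to the visit, whose protocol window is −1.5/+3 months. SAP Table 1 ends its 3-month period at 5 × 30.4 − 1 = 151 days, which may be later than many last contacts.

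**The case against.** The strongest reply is that the plan never says the denominator is all treated. SAP 7.1.3 defines who is analysed, SAP 7.4 says that only observed data are analysed, and SAP 4 ties the endpoints to visits, so a visit-based denominator is also possible. A reader might infer that the plan as written will produce a 12-month rate biased towards safety. The documents do not support that: the denominator is unstated, and the bias follows only on one reading. This part of the objection stands.

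SAP 7.1.3 also provides that data beyond 3 months will be summarised for subjects who already had them when the termination was announced. With SAP 5, this partly supplies the limit that SAP 4, 7.2.2 and 7.9.5 omit. The difference between 7.2.2 and 7.9.6 on secondary surgeries is then a general section lacking a qualifier that the specific one carries. That is a matter of wording, and it still needs aligning.

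The exit times are assumed. SAP 7.1.1 has subjects scheduled to the cut-off date, so some may be followed well past 3 months. The 20 are enrolled and available subjects, of whom 7.1.3 would drop any not given the device. The size of any bias is therefore not known.

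A reader might also take the removal of time-to-event estimation as an undisclosed change. It is not: SAP 3 and 7.12 disclose that analyses changed and why.

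What survives is the gap. Neither simple denominator gives a usable 12-month rate, and nothing in 7.1.3, 7.4 or SAP 5 says how a subject last seen at month 4 enters it.

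**Conclusion.** The plan promises a 12-month rate that it does not define and that the expected follow-up cannot support as a simple proportion. That conclusion rests only on the SAP's own numbers and on the absence of a rule.

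The downward bias is conditional on an all-treated denominator. Its size depends on event timing and exit times that the documents do not give. With 18 of 20 leaving early, the crude rate could be about a third of the truth (s = 0.25) or only about 9% too low (s = 0.9). The latter is plausible if procedure-related events cluster early.

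The consequence is limited. These summaries are descriptive with no test or decision rule, counts per period appear beside the rate, and the two expected completers are disclosed. It should still be corrected, because a 12-month rate can be quoted without those caveats and the remedy is cheap.

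**What to change.** - In SAP 7.2.2 and 7.9.5, replace the crude 12-month rate and cumulative figure with a listing of events after 3 months, as 7.9.8 does for other 12-month data, or with events per person-month and the person-time shown.
- For the 3-month rate, state the denominator and the end day used. Show the number still followed at that day and an exact 95% CI.
- Align the 12-month wording of SAP 4, 7.2.2 and 7.9.5 with the availability limit already in SAP 5, 7.9.6 and 7.9.7.

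The cost is a few sentences in the SAP and a few lines of code using event onset and last-contact dates. The downside is that there is no headline 12-month rate and the stated uncertainty is wide. For example, 2/20 at 3 months has an exact 95% CI of 1.2% to 31.7%. No events after month 3 in 18 to 72 person-months would leave an exact 97.5% upper limit of 0.205 to 0.051 events per person-month.
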